7.2 Information on the Risk of Smoking and Smoking Cessation Advice and Briefing

At the Screening visit, before enrollment at Day -2 and at Discharge on Day 6, each subject will be given during the same session i) information on the risks of smoking, ii) smoking cessation advice, and iii) briefing on P4M3.

The information on the risk of smoking and the advice on smoking cessation will take the form of a brief interview according to the WHO recommendations and of the Public Health Service [18, 19]. The briefing of subjects on P4M3 will address any intended or unintended beliefs that participants may have about P4M3. The goal of the briefing is to help ensure that subjects enter and exit the study with an accurate understanding of the product risks, including an understanding that ENDS have not been demonstrated to be less harmful than CIG.

Details of the sessions will be recorded in the source document file. These sessions will be given to the subjects on an individual basis during a face-to-face meeting between the subject and the PI(s) or designee(s) and may additionally be given in a group session.

Confidentiality Statement

Data and information contained in this document are considered to constitute trade secrets and confidential commercial information, and the legal protections provided to such trade secrets and confidential information are hereby claimed under the provisions of applicable law. No part of this document may be publicly disclosed without the written consent of Philip Morris Products S.A

7.3 Support during Abstinence from any Tobacco and Nicotine Containing Products

Subjects will be offered support during periods of abstinence from any TNP during the study by the Investigator and/or investigational site staff. Support resources will include counselling and assistance, entertainment, monitoring of the subject's behavior, and AEs.

7.4 Clinical and Other Assessments

The results of the clinical assessments described in this section will be recorded in the CRF.

Any clinically relevant medical condition detected during Screening visit assessments has to be documented as a concomitant disease. This also applies to clinically relevant findings in laboratory values, vital signs, spirometry, and ECGs detected during Screening visit assessments. Any untoward medical occurrence in a subject detected during the study which was not present at Screening visit must be documented as an AE. Worsening of a pre-existing condition from Screening visit onwards will also be documented as an AE.

7.4.1 Demographic Data

Sex, date of birth, and race will be recorded.

7.4.2 Medical History, Concomitant Disease, Previous and Concomitant Medications

Relevant medical history or any concomitant disease will be documented at the Screening visit. Medical history is defined as any condition that started and ended prior to the ICF signature at the Screening visit. A concomitant disease is defined as any condition that is either detected or is still ongoing at the time of ICF signature. The final status of any concomitant disease (i.e., stop date or ongoing) should be verified at each visit.

Prior medication taken within 4 weeks prior to the Screening visit and any concomitant medication will be documented. Any medication started prior to the Screening visit and still being taken by the subject will be considered concomitant medication. Medication initiated after the Screening visit will also be referred to as concomitant medication. The definition of concomitant medication applies to both prescribed and over-the-counter products.

Records of medication taken should include the drug name (preferably both generic and trade name), route of administration (e.g., oral, intravenous), dose and frequency (expressed in metric units, e.g., mg, mL, or IU), indication, and the start and, if applicable, the stop date (day, month, and year). Therapy changes (including changes of regimen) during the

Confidentiality Statement

Data and information contained in this document are considered to constitute trade secrets and confidential commercial information, and the legal protections provided to such trade secrets and confidential information are hereby claimed under the provisions of applicable law. No part of this document may be publicly disclosed without the written consent of Philip Morris Products S.A.

study will be documented. If a concomitant medication is still being taken by the subject at the end of the study, this will be recorded in the CRF.

7.4.3 Physical Examination

A physical examination will include review of general appearance, hair and skin, head, eyes, ears, nose and throat, neck, thyroid gland, chest, lungs, back, abdomen, dentition, gastrointestinal, cardiovascular, musculoskeletal and neurological systems. The physical examination is to be conducted by the Investigator or designated fully trained representative.

For those results outside of the normal range, the Investigator will determine appropriate follow-up including reporting of any AEs.

7.4.4 Body Height and Weight

Body weight and height will be recorded at the Screening Visit, body weight will also be recorded at Admission Visit Day -2.

The BMI will be calculated from the body weight and height using the following formula:

$$\text{BMI} = \frac{\text{weight in kilograms}}{\text{height in meters}^2} = \frac{kg}{m^2}$$

The BMI will be used to assess eligibility for enrolment.

7.4.5 Vital Signs

Vital signs will include systolic and diastolic blood pressure, respiratory rate and pulse rate.

All parameters will be recorded in supine position after the subject has rested for at least 5 minutes. Subjects should have abstained from using any TNP for at least 15 minutes prior to Vital signs assessment.

For those results outside of the normal range, the Investigator will determine appropriate follow-up including reporting of any AEs.

7.4.6 Spirometry

Spirometry will be performed at the Screening visit, at Baseline visit Day -1, and at Discharge (Day 6), or Early termination, in accordance with the 2019 guideline of the American Thoracic Society (ATS)/European Respiratory Society (ERS) Joint Task Force on the standardization of spirometry [20, 21]. Spirometry predicted values will be

Confidentiality Statement

Data and information contained in this document are considered to constitute trade secrets and confidential commercial information, and the legal protections provided to such trade secrets and confidential information are hereby claimed under the provisions of applicable law. No part of this document may be publicly disclosed without the written consent of Philip Morris Products S.A

standardized to the National Health and Nutrition Examination Survey III predicted set [22].

Assessed parameters will include: FEV₁, FEV₁ % predicted, FVC, FVC % predicted and FEV₁/FVC.

All personnel performing spirometry testing should have the appropriate training and quality control measures should be put into place and be properly documented. The testing will be performed in sitting position at rest for at least 15 minutes and at least 1 hour after smoking CIG (Screening visit).

For those results outside of the normal range, the Investigator will determine appropriate follow-up including reporting of any AEs.

Any printouts of Spirometry on thermo-sensitive paper must be photocopied and stapled together for inclusion in the source documents.

7.4.7 Electrocardiogram

A standard 12-lead ECG will be recorded after the subject has rested for at least 10 minutes in supine position.

All ECGs will be reviewed on an ongoing basis by the Investigator or designee. The following parameters will be documented: heart rate, PR interval, QRS interval, QT interval, and QTc interval corrected according to Fridericia's formula.

For those results outside of the normal range, the Investigator will determine appropriate follow-up including reporting of any AEs.

Any printouts of ECGs on thermo-sensitive paper must be photocopied and stapled together for inclusion in the source documents.

7.4.8 Biomarker Assessment

All bioanalytical assays and laboratory assessments will be carried out using validated methods (sections 7.5 and 7.6). The bioanalytical methods used will be documented in the respective bioanalytical plans/reports. A list of laboratories is provided in Appendix B.

Blood samples and 24-hours urine samples will be collected according to the assessment schedule (Appendix A) to measure Biomarkers of Exposure to nicotine and some HPHC:

- In blood: carboxyhemoglobin (% of saturation of hemoglobin)
- In 24-hours urine: 3-HPMA, 2CyEMA, NNAL, S-PMA, 3-HMPMA, total NNN, 2-HPMA, 3-OH-B[a]P, DHPMA, NEQ, Cd, Cr, Pb, and Ni (creatinine normalization)

Confidentiality Statement

Data and information contained in this document are considered to constitute trade secrets and confidential commercial information, and the legal protections provided to such trade secrets and confidential information are hereby claimed under the provisions of applicable law. No part of this document may be publicly disclosed without the written consent of Philip Morris Products S.A

7.4.9 Laboratory Assessments

Clinical Chemistry, Hematology, and Urine Analysis for Safety Panel

Subjects should have fasted for at least 6 hours prior to hematology and clinical chemistry analyses, except at Screening visit and Early termination where non-fasting samples can be used. Tests will be conducted at a local laboratory (see [Appendix B](#)). If during the screening period a blood sample is not suitable for analysis (e.g., blood clotting) a re-test should be performed for the specific parameters which are not available. Safety urine analysis will be also assessed.

Parameters to be tested are listed in ([Appendix D](#)).

Serology

At the Screening visit, tests for hepatitis B virus, hepatitis C virus, and human immunodeficiency virus (anti-HIV1/2) will be performed.

CYP1A2

CYP1A2 activity will be assessed in plasma by measuring paraxanthine (PX) and caffeine (CAF) concentrations and calculating the PX/CAF molar metabolic ratio [23] on Baseline Day -1 and Day 5. Samples to measure PX and CAF will be drawn approximately 6 hours (± 15 minutes) after the intake a caffeine tablet (approx. 200 mg caffeine). The exact time of intake of caffeine tablet in the morning and of the time of blood sampling must be recorded.

Urine Drug Screening

At Screening visit and on Admission Day -2, a urine drug screen will be performed. The urine will be screened for amphetamine type substances, barbiturates, benzodiazepines, cannabinoids, cocaine, and opiates.

In case of a positive urine drug test, a re-test will not be allowed to evaluate eligibility. In case of an inconclusive test, a re-test can be performed but this needs to be done immediately after the inconclusive test.

Urine Cotinine Screening

A urine cotinine test will be performed to confirm the nicotine/tobacco use status.

Confidentiality Statement

Data and information contained in this document are considered to constitute trade secrets and confidential commercial information, and the legal protections provided to such trade secrets and confidential information are hereby claimed under the provisions of applicable law. No part of this document may be publicly disclosed without the written consent of Philip Morris Products S.A.

The test must detect cotinine with a threshold of ≥ 200 ng/mL. In case of a negative cotinine test, a re-test will not be allowed to evaluate eligibility. In case of an inconclusive test, a re-test can be performed but this needs to be done immediately after the inconclusive test.

Alcohol Test

An alcohol breath test will be performed.

Serum Pregnancy Test

A serum pregnancy test will be performed for all female subjects. Subjects with a positive pregnancy test or unclear results (from one repetition) before product testing and enrolment will be considered as screen failures. In case of any positive pregnancy test, the Investigator or designee will inform the subject about the risks associated with smoking during pregnancy and subjects will be referred to health care facility/health care provider for pregnancy follow-up.

All pregnancies detected during the study must be reported and handled as described in section 8.5.

7.4.10 Sample Handling, Storage, and Shipment

Urine drug tests and urine cotinine tests, as well as all safety panel tests and pregnancy tests, will be done by the site personnel at the site. All other blood and urine samples will be managed by the laboratory designated in [Appendix B](#).

Detailed procedures for handling of samples will be described in the sample handling manual (SHM). Safety laboratory samples will be destroyed as per laboratory local regulations. All other samples (except biobanking samples) will be destroyed after the Clinical Study Report (CSR) has been finalized. The facilities at which the samples are stored will be informed in writing by the Sponsor when destruction of the samples shall be performed.

Blood Samples

Blood samples will be drawn by qualified and trained site personnel and according to the standard operating procedures (SOPs) at the investigational site.

Since the test for nicotine concentration is highly sensitive, precautions should be taken during blood sampling and processing to prevent the contamination of samples with environmental nicotine.

Confidentiality Statement

Data and information contained in this document are considered to constitute trade secrets and confidential commercial information, and the legal protections provided to such trade secrets and confidential information are hereby claimed under the provisions of applicable law. No part of this document may be publicly disclosed without the written consent of Philip Morris Products S.A.

In total, approximately 81 mL of blood will be collected for this study including samples for determination of CYP1A2 activity (10 mL), COHb (30 mL) and safety laboratory (approximately 40.5 mL). This calculation is based on an individual volume of each sample of 5 mL for CYP1A2 analysis, 13.5 mL per safety laboratory assessments (including serology and pregnancy test), and 5 mL for COHb assessment. The total volume of blood drawn (approximately 81 mL) will not exceed the levels for a standard blood donation.

Details on the procedures for collection, labelling, processing, and shipment of samples will be described in the SHM.

Urine Samples

Spot urine samples will be used for the urine drug screen, urine cotinine screen, and safety urine analysis at Screening visit and Baseline visit on Day -1, and after completion of 24-hour urine sample collection on Day 6.

24-hour urine collection Subjects will discard their first void in the morning of Day -1. The collection period will start immediately after. After 24-hours \pm 1h of urine collection, subjects will empty their bladder again in the morning of the visit and this urine will be used as the final portion of the 24-hour urine sample.

During the collection period, all urine passed must be collected in the sampling container. No urine should be passed into the toilet. The start and the end time of urine collection will be recorded by the subject and checked by the site staff. The volume of 24-hour urine will be measured by the site staff upon collection of urine containers from the subjects. For assessment of urine BoExp, creatinine aliquots from the 24-hour urine collection will be taken. In the schedule of events for the 24-hour urine collection, the dot corresponds to the day on which the 24-hour urine collection period starts.

Biobanking of urine If a subject gives additional consent for biobanking, additional samples of urine from the 24-hour collection will be collected, i.e., from the daily collections commencing Day -1, 1, 2, 3, 4, and 5. The samples intended for biobanking will be kept frozen and will be shipped to a central storage facility according to the SHM. After the final CSR is signed, samples of urine will be stored for a maximum duration of 2 years.

7.5 Other Study Procedures

7.5.1 Demonstration P4M3 and Product Test

All subjects will have a demonstration of P4M3 by the investigational site staff at the Screening visit without product use.

Confidentiality Statement

Data and information contained in this document are considered to constitute trade secrets and confidential commercial information, and the legal protections provided to such trade secrets and confidential information are hereby claimed under the provisions of applicable law. No part of this document may be publicly disclosed without the written consent of Philip Morris Products S.A

At Admission (Day -2), after enrolment, investigational site staff will inform subjects on product use and subjects will have a product test with P4M3 *ad libitum* for a duration of approximately 10 minutes per flavor.

7.5.2 Human Puffing Topography Assessment

Human puffing topography (HPT) involves the measurement of each subject's unique way of using P4M3.

The miniaturized detachable external data recorder (MDED R) puffing topography device measures and records the flow rate, other per-puff parameters, and power setting of P4M3 as listed in [Appendix C](#). From the per-puff measurements, per-day parameters will be derived.

The MDED R puffing topography device will be used with the P4M3 on Day 1 to Day 5 with data recording during *ad libitum* use. Data will not be collected during CIG smoking.

The P4M3 is equipped with a pressure sensor, which measures the pressure at the Cartridge level. When a puff is drawn, the P4M3 calculates the difference of pressure between the atmospheric pressure and the pressure measured at the Cartridge level. The aerosol production (heating cycle) is then triggered based on the difference of pressure values calculated by the P4M3. The MDED R puffing topography device allows to collect these data when it is mechanically attached to the Battery Unit of P4M3 and electronically connected to its USB port. The MDED R puffing topography device works as a data logger. Once connected to the P4M3, the MDED R puffing topography device will record HPT data. Any malfunction of the MDED R puffing topography device will be documented in the appropriate log.

One MDED R puffing topography device will be assigned at Day -1 for each subject and will be used for all further HPT assessments. A replacement device will be provided in case of malfunction of the device assigned. The Sponsor will provide training on the use of the MDED R puffing topography device to the investigational site staff which will be responsible for the HPT assessment. All MDED R puffing topography devices will be returned to the Sponsor after completion of the study.

Prior to calculation of the parameters, the Sponsor's HPT group will process, validate, and discard any invalid data, as per the Sponsor's SOPs. The Sponsor will provide copies of both the raw and validated HPT datasets to the Investigator. Only valid data will be part of the study database and will be analyzed.

Confidentiality Statement

7.5.3 Weighing of P4M3 Cartridge

P4M3 Cartridges will be weighed by the study personnel before and after daily product use by the subjects to estimate the amount of liquid used, to calculate delivered nicotine.

The weight will be determined with a scale with an accuracy of 1 mg.

7.6 Questionnaires

The questionnaires will be completed by the subjects ([Appendix A](#)). All subject-reported measures as well as instructions will be provided in the subject's local language.

7.6.1 Nicotine/Tobacco Product Use History

At the Screening visit and at Admission (Day -2), subjects will be asked questions about their TNP use history. The questions will capture frequency and quantity TNP use over the past 4 weeks, and number of continuous years of CIG smoking. This information will be used as characteristics of the study subjects, to assess their eligibility to participate in the study, and to serve as baseline values.

7.6.2 Fagerström Test for Nicotine Dependence (Revised Version)

Self-reported level of nicotine dependence will be assessed via a questionnaire on Baseline Day -1 using the Fagerström Test for Nicotine Dependence (FTND) in its revised version [\[24\]](#).

The questionnaire consists of six questions which will be answered by the subjects themselves. The scores obtained on the test permit the classification of nicotine dependence into three levels: Mild (0-3 points), moderate (4-6 points), and severe (7-10 points) [\[24\]](#). This information will be used as characteristics of the study subjects.

7.6.3 ABOUT – Product Experience Questionnaire

Product experience will be assessed via a subject self-reported outcome measure, part of the ABOUT toolbox [\[25\]](#).

The questionnaire consists of 3 multi-item scales and 2 single-item scales, arising from an adaptation and rewording of the modified cigarette evaluation questionnaire (mCEQ) [\[26\]](#) to RRP and the Product Evaluation Scale [\[27\]](#).

The questionnaire assesses the degree to which subjects experience the reinforcing effects of P4M3 Gen 2.0 with CA35 and CM 35 Cartridges use in CIG smokers switching to P4M3 compared to subjects continuing CIG smoking by measuring:

Confidentiality Statement

Data and information contained in this document are considered to constitute trade secrets and confidential commercial information, and the legal protections provided to such trade secrets and confidential information are hereby claimed under the provisions of applicable law. No part of this document may be publicly disclosed without the written consent of Philip Morris Products S.A.

- Product satisfaction (satisfying, tastes good, enjoy the product).
- Psychological rewards (calms down, more awake, less irritable, helps concentrate, reduces hunger).
- Aversion (dizziness, nausea).
- Enjoyment of respiratory tract sensations (single-item assessment).
- Craving reduction (single-item assessment).

Subjects will be asked to assess the items of the questionnaire on a 7-point scale, ranging from “not at all” to “extremely”. A score for each subscale will be computed based on the scoring rule established by the questionnaire developer [26].

Symptoms or worsening of symptoms documented in the questionnaire do not need to be documented as additional AEs as the main source for AE collection is the face-to-face interview between the subject and study site staff, using open, non-directive questions, as described in section 8.2.

Confidentiality Statement

Data and information contained in this document are considered to constitute trade secrets and confidential commercial information, and the legal protections provided to such trade secrets and confidential information are hereby claimed under the provisions of applicable law. No part of this document may be publicly disclosed without the written consent of Philip Morris Products S.A

8 Adverse Events

8.1 Definitions

8.1.1 Adverse Events

An adverse event (AE) is defined as any health-related event which is adverse or unfavorable and which either starts after ICF signature or represents a worsening of a health-related condition that existed at the time of that signature. Careful medical judgment is required to establish whether a clinical finding (including an abnormal laboratory result) is a true AE or just a manifestation of a preexisting health-related condition. An AE may or may not have a causal relationship with the study procedures or with the use of investigational product.

8.1.2 Serious Adverse Events

A serious adverse event (SAE) is defined as an AE that:

- results in death,
- is life-threatening,
- requires inpatient hospitalization or prolongation of existing hospitalization,
- results in persistent or significant disability/incapacity,
- is a congenital anomaly/birth defect, or
- is an important medical event

Important medical events that may not result in death, be life-threatening, or require hospitalization may be considered an SAE when, based on appropriate Investigator's medical judgment, they may jeopardize the subject, or the subject may require medical or surgical intervention to prevent one of the outcomes listed in the above definitions.

"Life-threatening" means that the subject was at immediate risk of death from the event. It might have caused death if it had occurred in a more serious form.

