8.2.3 Intensity of Adverse Event

The Investigator must assess the intensity of each reported AE according to the following grading scale:

Table 8 Intensity of Adverse Events

Mild:	Easily tolerated, not interfering with normal everyday activities
--------------	---

Confidentiality Statement

Data and information contained in this document are considered to constitute trade secrets and confidential commercial information, and the legal protections provided to such trade secrets and confidential information are hereby claimed under the provisions of applicable law. No part of this document may be publicly disclosed without the written consent of Philip Morris Products S.A

Moderate:	Interferes with normal everyday activities, but the subject is still able to function
Severe:	Incapacitating and requiring medical intervention

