8.3 Reporting of Serious Adverse Events

Any SAE observed during the period of collection in this study must be reported within 24 hours of first awareness to Sponsor, via email, having the SAE form attached.

Follow-up information should be reported on a new SAE report form, marked as a follow-up report, and submitted to Sponsor according to the same timelines as described above. The follow-up SAE report form must include the minimum information required for form completion and only changed/new information needs to be specified. Information provided in the follow-up SAE report form supersedes any information that was initially reported.

The Investigator or designee is responsible for submitting the relevant reports of SAEs that occur during the study to the IEC, according to local regulations.

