#### 9.6.5.1.1 Serious Adverse Events (Including Deaths)

The number and percentages of SAEs will be summarized overall and by SOC and PT for each randomized study arm or a group of enrolled but not randomized subjects when applicable, for the SAF. Tabulations will include both the number of subjects experiencing an event and the number of events.

Unless specified otherwise, results will be sorted alphabetically by SOC, and by decreasing frequency of the PTs within a SOC. In the event of PTs having equal frequencies, the PTs will be sorted alphabetically within the SOC.

The number and percentage of deaths will be presented if applicable and AEs leading to death will be listed.

All SAE data will be listed.

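### Protocol 8.1.2 defines a life-threatening event by two tests of different breadth and does not say how they combine, so events with no actual risk of death can be classed as SAEs

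*Protocol*

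**What the plan says.** Protocol section 8.1.2 lists six criteria, any one of which makes an AE serious. One is that the event "is life-threatening". The section then explains that term in two consecutive sentences. The first says it "means that the subject was at immediate risk of death from the event". The second says of the event: "It might have caused death if it had occurred in a more serious form". The second sentence is affirmative and has no connecting word to the first.

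The same section has a separate route that rests on medical judgment: "Important medical events that may not result in death, be life-threatening, or require hospitalization may be considered an SAE when" the investigator considers that the subject may be jeopardized or may need intervention to prevent one of the listed outcomes.

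SAE status is then used in several places:
- Protocol 8.3: "Any SAE observed during the period of collection in this study must be reported within 24 hours of first awareness to Sponsor". The investigator also submits SAE reports to the ethics committee as local regulations require.
- Protocol 8.2.6: a non-serious AE still ongoing when the 3-day follow-up ends is closed with an unknown outcome. An SAE is followed beyond that point until it resolves, stabilizes or is explained.
- SAP 9.6.5.1.1: "The number and percentages of SAEs will be summarized overall and by SOC and PT", by study arm in the safety set.

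**The concern.** A definition used to classify individual events should give one test. Here an investigator has two, and the second is easier to meet than the first. An event that put nobody in danger can still be one that, in a worse form, might have killed. If the second sentence is taken as sufficient, such an event is an SAE by definition. If the first sentence governs, it is not.

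Two investigators with the same facts and the same protocol could therefore classify one event differently, and so could one investigator on two occasions. Its reporting deadline, its follow-up and its place in the SAE tables would differ accordingly. SAE incidence is a listed safety endpoint (Protocol 3.2.2), so the classification reaches the study report.

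**Working it through.** There is no figure to reproduce and no arithmetic applies. The check is a reading of the two sentences together and a search for anything that settles how they combine.

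**Step 1: compare the two tests.** Let A be the events that put the subject at immediate risk of death as they occurred (first sentence). Let B be the events that might have caused death in a more serious form (second sentence). An event in A would ordinarily also be in B. The reverse does not hold.

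**Step 2: go through the possible roles of the second sentence.**

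| Role of the second sentence | Events that count as life-threatening | Change against the first sentence alone |
|---|---|---|
| Further condition (A and B) | A | None; the sentence is idle |
| Alternative (A or B) | B | Adds events in B that are not in A |
| Explanation of the term | B | Adds events in B that are not in A |

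So the sentence either does nothing or widens the category. As an affirmative statement it never narrows it.

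**Step 3: try it on events the protocol anticipates.** Fainting is named in Protocol 2.3.2 as a risk of blood sampling. Suppose a subject faints briefly and recovers, with no immediate risk of death. Under the first sentence the event is not life-threatening. If one accepts that fainting has a more serious, possibly fatal form (an assumption), it is in B, and under the second or third role it becomes an SAE. Irritability, named in Protocol 2.3.3 as a withdrawal symptom, has no obvious fatal form and is not an SAE under any role. The widening is real, but it has limits.

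**Step 4: compare with the rest of the section.** The important-medical-event route leaves events that were not life-threatening to the investigator's judgment. Under the wider roles, some of these would become SAEs automatically, without that judgment. The protocol also keeps seriousness apart from intensity: section 8.2.1 records them as separate items, and section 8.2.3 says "The Investigator must assess the intensity of each reported AE according to the following grading scale". The second sentence decides seriousness by imagining a greater intensity than was observed. Both points fit the first sentence better than the second.

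**Step 5: look for a correction elsewhere.** Protocol 8.1.3 refers back to the seriousness criteria and so inherits the problem. Protocol 8.2.1, 8.2.3, 8.2.6 and 8.3 use the SAE and intensity categories without redefining life-threatening. SAP 9.6.5.1, 9.6.5.1.1 and 10.2 give no SAE definition. Nothing settles the role of the second sentence.

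**The case against.** The strongest reply is that the first sentence is the operative one, because it states what the term means. The second has no word that makes it a separate sufficient test. Read together, the two leave the set of SAEs as the first sentence has it. This stands as far as it goes: the sentences do not strictly contradict each other, since one event can satisfy both. It does not remove the problem, because the protocol does not state that reading, and on that reading the second sentence has no purpose.

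A second reply is that the consequences are small. Safety endpoints are descriptive only (Protocol 12.6.2; SAP 9.6.3.2). AEs are also tabulated whether or not they are serious, and all SAE data are listed (SAP 9.6.5.1 and 9.6.5.1.1), so a reader could notice a minor event labelled serious. The error runs toward over-reporting and does not hide harm. The important-medical-event route already lets an investigator class some of these events as SAEs. All of this stands and limits the size of the point.

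Four stronger readings are tempting, and the documents do not support them:
- *Almost any AE becomes an SAE.* This needs the second sentence applied alone, and even then only events with a plausibly fatal worse form qualify.
- *A negation was dropped.* The sentence would work as an exclusion, so this is a reasonable guess, but nothing in the documents shows it.
- *The effect is 1/18 = 5.6 percentage points in an arm, or 1/36 = 2.8 in the combined P4M3 arms.* That is one subject divided by the planned arm size. It holds for any single reclassified subject from any cause and does not estimate the effect of this wording.
- *The arms cannot be compared on SAEs.* The study is open-label, but nothing indicates that investigators would apply the sentence differently by arm.

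**Conclusion.** Wrong as written. Protocol 8.1.2 sets an actual-risk test and a wider hypothetical test for the same term and leaves their relation open. On two of the three possible roles for the second sentence, events that carried no actual risk of death become SAEs. The result can be inconsistent 24-hour reporting, inconsistent follow-up after the 3-day period and inconsistent counts in the descriptive SAE tables.

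No number of affected events can be given, because the documents contain no expected AE or misclassification rate. The conclusion rests on the protocol's own wording and on two assumptions: that an event with actual immediate risk would also meet the hypothetical test, and that at least some anticipated AEs have a fatal worse form without having put the subject at risk. The biomarker analyses, the testing sequence, alpha, power and sample size are untouched.

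**What to change.** Reconcile the two sentences in Protocol 8.1.2 so that only actual, immediate risk of death from the event as it occurred defines life-threatening. Either of two edits does this:
- delete the second sentence; or
- reword it as an explicit exclusion, stating that an event which might have been fatal only in a hypothetical, more serious form does not meet the criterion.

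Then check that the SAE form instructions agree; they are not among the documents reviewed. If any event has already been classed as serious solely because it was judged life-threatening, re-examine it against the clarified text before database lock.

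No important event is lost, because the important-medical-event criterion stays as it is. The cost is one sentence, a check of the form instructions and a protocol amendment, which under Protocol 1.1 goes to the ethics committee. No assessment, analysis or program changes.
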